8.1 TRIAL APPROVAL, PATIENT INFORMATION, AND INFORMED CONSENT

This trial will be initiated only after all required legal documentation has been reviewed and approved by the respective Institutional Review Board (IRB) / Independent Ethics Committee (IEC) and competent authority (CA) according to national and international regulations. The same applies for the implementation of changes introduced by amendments.

Prior to patient participation in the trial, written informed consent must be obtained from each patient (or the patient's legally accepted representative) according to ICH / GCP and to the regulatory and legal requirements of the participating country. Each signature must be personally dated by each signatory and the informed consent and any additional patient-information form retained by the Investigator as part of the trial records. A signed copy of the informed consent and any additional patient information must be given to each patient or the patient's legally accepted representative.”

The following paragraph pertains to Japan only:

The Investigator must give a full explanation to trial patients including the items listed below in association with the use of the patient information form, which is prepared avoiding the use of technical terms and expressions. The patient is given sufficient time to consider participation in the trial. The Investigator obtains written consent of the patient's own free will with the informed consent form after confirming that the patient understands the contents. The Investigator must sign (or place a seal on) and date the informed consent form. If a trial collaborator has given a supplementary explanation, the trial collaborator also signs (or places a seal on) and dates the informed consent.

Re-consenting may become necessary when new relevant information becomes available and should be conducted according to the sponsor's instructions.

8.2 DATA QUALITY ASSURANCE

A quality assurance audit/inspection of this trial may be conducted by the Sponsor, Sponsor's designees, or by IRB / IEC or by regulatory authorities. The quality assurance auditor will have access to all medical records, the Investigator's trial-related files and correspondence, and the informed consent documentation of this clinical trial.

8.3 RECORDS

Case Report Forms (CRFs) for individual patients will be provided by the sponsor via remote data capture. See [Section 4.1.5.2](#) for rules about emergency code breaks. For drug accountability, refer to [Section 4.1.8](#).

8.3.1 Source documents

Source documents provide evidence for the existence of the patient and substantiate the integrity of the data collected. Source documents are filed at the investigator's site.

Data reported on the CRF must be consistent with the source data or the discrepancies must be explained. The Investigator may need to request previous medical records or transfer records, depending on the trial; current medical records must also be available. For eCRFs all data must be derived from source documents.

8.3.2 Direct access to source data and documents

An adaptive approach to clinical trial monitoring will be utilised. This is initiated by an assessment of the risk associated with the trial combined with identification of critical data and processes. An Integrated Quality and Risk Management Plan documents the strategies involved with the implementation of onsite, offsite and central monitoring activities in order to direct focus to the areas of greatest risk which have the most potential impact to patient safety and data quality. Trial oversight is achieved by regular review of a report of risk, which then influences any monitoring adaptations.

The Investigator / institution will permit trial-related monitoring, audits, IRB / IEC review and regulatory inspection, providing direct access to all related source data / documents. eCRF and all source documents, including progress notes and copies of laboratory and medical test results must be available at all times for review by the Sponsor's clinical trial monitor, auditor and inspection by health authorities (e.g. FDA). The Clinical Research Associate (CRA) / on site monitor and auditor may review all eCRF, and written informed consents.

8.3.3 Storage period of records (Applicable to Japan only)

Trial site(s):

The trial site(s) must retain the source documents and essential documents for a period defined by the Japanese GCP regulation and trial site's contract with the sponsor.

Sponsor:

The Sponsor must retain the essential documents according to the Sponsor's SOPs. When it is no longer necessary for the trial site to retain the source documents and essential documents, the Sponsor must notify the head of trial site.

8.4 LISTEDNESS AND EXPEDITED REPORTING OF ADVERSE EVENTS

8.4.1 Listedness

To fulfil the regulatory requirements for expedited safety reporting, the Sponsor evaluates whether a particular adverse event is "listed", i.e. is a known side effect of the drug or not. Therefore, a unique reference document for the evaluation of listedness needs to be provided. For the study drug BI 655066, this is the current version of the Investigator's Brochure ([c01569420-06](#)), which is provided in the ISF.

No AEs are classified as listed for matching placebo, trial design, or invasive procedures

8.4.2 Expedited reporting to health authorities and IEC / IRB

Expedited reporting of serious adverse events, e.g. suspected unexpected serious adverse reactions (SUSAR) to health authorities and IEC / IRB, will be done according to local regulatory requirements.

8.5 STATEMENT OF CONFIDENTIALITY

Individual patient medical information obtained as a result of this trial is considered confidential and disclosure to third parties is prohibited with the exceptions noted below. Patient confidentiality will be ensured by using patient identification code numbers. Treatment data may be given to the patient's personal physician or to other appropriate medical personnel responsible for the patient's welfare. Data generated as a result of the trial need to be available for inspection on request by the participating physicians, the Sponsor's representatives, by the IRB / IEC and the regulatory authorities.

8.6 END OF TRIAL

The end of the trial is defined as written in [Section 6.2.3](#).

The IEC / competent authority in each participating EU member state will be notified about the end or early termination of the trial.

For Japan: When the trial is completed, the Investigator should inform the head of the trial site of the completion in writing, and the head of the trial site should promptly inform the IRB and Sponsor of the completion in writing.

8.7 PROTOCOL VIOLATIONS

This Section is applicable to Japan only

The investigator should document any deviation from the protocol regardless of their reasons. Only when the protocol was not followed in order to avoid an immediate hazard to trial patients or for other medically compelling reason, the principal investigator should prepare and submit the records explaining the reasons thereof to the sponsor, and retain a copy of the records.

Proprietary confidential information © 2016 Boehringer Ingelheim International GmbH or one or more of its affiliated companies

**8.8 COMPENSATION AVAILABLE TO THE PATIENT IN THE EVENT OF
TRIAL RELATED INJURY**

This Section is applicable to Japan only

In the event of health injury associated with this trial, the Sponsor is responsible for compensation based on the contract signed by the trial site.

10 APPENDICES

10.1 PASI DEFINITIONS AND USE

The PASI is an established measure of clinical efficacy for psoriasis medications. ([R96-3541](#)) The PASI is a tool that provides a numeric scoring for patients overall psoriasis disease state, ranging from 0 to 72. It is a linear combination of percent of surface area of skin that is affected and the severity of erythema, infiltration, and desquamation over four body regions.

The endpoints used are based on the percent reduction from baseline, generally summarized as a dichotomous outcome based on achieving over an X% reduction (or PASI_X), where X is 50, 75, 90 and 100.

To calculate the PASI, the four main body areas are assessed: **head (h), trunk (t), upper extremities (u) and lower extremities (l)**. These correspond to 10, 30, 20 and 40% of the total body area respectively.

The **area of psoriatic involvement** of these four areas (Ah, At, Au, and Al) is given a numerical value: 0 = no involvement, 1 = <10%, 2 = 10 to <30%, 3 = 30 to <50%, 4 = 50 to <70%, 5 = 70 to <90%, and 6 = 90 to 100% involvement.

The **signs of severity, erythema (E), infiltration (I) and desquamation (D)** of lesions are assessed using a numeric scale 0-4 where 0 is a complete lack of cutaneous involvement and 4 is the severest possible involvement; scores are made independently for each of the areas, h, t, u and l and represents a composite score for each area. An illustration of judging erythema follows: 0 = no erythema, 1 = slight erythema, 2 = moderate erythema, 3 = striking erythema, and 4 = exceptionally striking erythema.

The PASI score is calculated according to the following formula:

$$\text{PASI} = 0.1(\text{Eh}+\text{Ih}+\text{Dh})\text{Ah} + 0.3(\text{Et}+\text{It}+\text{Dt})\text{At} + 0.2(\text{Eu}+\text{Iu}+\text{Du})\text{Au} + 0.4(\text{El}+\text{Il}+\text{Dl})\text{Al}$$

10.2 STATIC PHYSICIAN GLOBAL ASSESSMENT (SPGA)

The sPGA is a 5 point score ranging from 0 to 4, based on the physician's assessment of the average thickness, erythema, and scaling of all psoriatic lesions ([R15-5200](#)).

The assessment is considered "static", which refers to the patients disease state at the time of the assessments, without comparison to any of the patient's previous disease states, whether at Baseline or at a previous visit.

A lower score indicates less body coverage, with 0 being clear and 1 being almost clear.

Erythema

- 0 Normal (post-inflammatory hyper/hypopigmentation may be present)
- 1 Faint, diffuse pink or slight red coloration
- 2 Mild (light red coloration)
- 3 Definite red coloration (Dull to bright red)
- 4 Bright to Deep red coloration of lesions

Induration (plaque elevation)

- 0 None
- 1 Just detectable (slight elevation above normal skin)
- 2 Mild thickening (slight but definite elevation, typically edges are indistinct or sloped)
- 3 Clearly distinguishable to moderate thickening (marked definite elevation with rough or sloped edges)
- 4 Severe thickening with hard edges (marked elevation typically with hard or sharp edges)

Scaling

- 0 No scaling
- 1 Minimal focal scaling (surface dryness with some desquamation)
- 2 Predominately fine scaling (fine scale partially or mostly covering lesions)
- 3 Moderate scaling (coarser scale covering most or all of the lesions)
- 4 Severe /coarse scaling covering almost all or all lesions (coarse, non-tenacious scale predominates)

Scoring:

Clear	0 = 0 for all three
Almost clear	1 = mean $>0, <1.5$
Mild	2 = mean $\geq 1.5, <2.5$
Moderate	3 = mean $\geq 2.5, <3.5$
Severe	4 = mean ≥ 3.5

sPGA Rating Scale for Overall Psoriatic Disease

Score	Short description	Detailed description
0	clear	No signs of psoriasis. Post-inflammatory hyper/hypopigmentation may be present
1	Almost clear	Normal to pink coloration; Just detectable (possible slight elevation above normal skin) No to minimal focal scaling
2	mild	Pink to light red coloration Mild thickening (slight but definite elevation, typically edges are indistinct or sloped) Predominantly fine scaling
3	moderate	Dull to bright red coloration Clearly distinguishable to moderate thickening Moderate scaling
4	severe	Bright to deep dark red coloration; Severe thickening with hard edges Severe coarse scaling covering almost all or all lesions

The scale used was static, i.e., it referred exclusively to the patient's disease state at the time of the assessments, without comparison to any of the patient's previous disease states, whether at Baseline or at a previous visit.

10.3 NAPSI – NAIL PSORIASIS SEVERITY INDEX

The NAPSI assesses how much of the fingernail is affected with psoriasis with scores ranging from 0 to 80. [\(R16-2654\)](#)

If a patient has nail psoriasis, the physician will assess the nail psoriasis at each protocol defined time point. Fingers (5) on each hand will be individually examined for two distinct assessments and are graded as follows:

Nail Matrix Assessment:

- 0 = None
- 1 = present in 1 quadrant of nail
- 2 = present in 2 quadrants of nail
- 3 = present in 3 quadrants of nail
- 4 = present in 4 quadrants of nail

Nail Bed Assessment:

- 0 = None
- 1 = present in 1 quadrant of nail
- 2 = present in 2 quadrants of nail
- 3 = present in 3 quadrants of nail
- 4 = present in 4 quadrants of nail

The sum of the scores will be added resulting a range of 0 to 80. If an individual finger assessment is missing (not done), the average of the remaining measured digits will be imputed and added to the sum. If < 50% of the finger assessments are missing the imputation will be performed. If more than 50% of the assessments are missing then the sum of the scores will be left as missing.

10.4 PPASI – PALMOPLANTAR PSORIASIS SEVERITY INDEX

The PPASI provides a numeric scoring for psoriasis affecting the hands and feet with scores ranging from 0 to 72. It is a linear combination of percent of surface area of hands and feet that are affected and the severity of erythema, induration, and desquamation.

If a patient has palmoplantar psoriasis, the physician will assess the psoriasis at each protocol defined time point. Both palms and soles on each hand and foot will be individually assessed for erythema, induration, desquamation and percentage of area affected as follows:

Erythema, Induration and Desquamation:

- 0 = None
- 1 = Slight
- 2 = Moderate
- 3 = Severe
- 4 = Very Severe

Percent of Palm and Sole Area Covered:

- 0 = Clear
- 1 = <10%
- 2 = 10-29%
- 3 = 30-49%
- 4 = 50-69%
- 5 = 70-89%
- 6 = 90-100%

The PPASI is a composite score and will be computed for each palm and sole, left and right and is derived from the sum of the scores for erythema (E), induration (I) and desquamation (D) multiplied by the score recorded for the extent of palm and sole area involved. PPASI is calculated as follows: (sum of scores for E+I+D)*Area *0.2(location: right palm) + (sum of scores for E+I+D)*Area *0.2(location: left palm) + (sum of scores for E+I+D)*Area *0.3(location: right sole) + (sum of scores for E+I+D)*Area *0.3(location: left sole). The range is 0 to 72.

Proprietary confidential information © 2016 Boehringer Ingelheim International GmbH or one or more of its affiliated companies

10.5 PSORIASIS SCALP SEVERITY INDEX (PSSI)

If a patient has scalp psoriasis, the physician will assess the erythema (redness), induration (hardness), desquamation (shedding of skin) and percent of scalp covered at each protocol defined time point. [\(R16-2653\)](#).

Erythema, Induration and Desquamation:

- 0 = None
- 1 = Slight
- 2 = Moderate
- 3 = Severe
- 4 = Very Severe

Percent of Scalp Covered:

- 1 = <10%
- 2 = 10-29%
- 3 = 30-49%
- 4 = 50-69%
- 5 = 70-89%
- 6 = 90-100%

The PSSI is a composite score derived from the sum of the scores for erythema, induration and desquamation multiplied by the score recorded for the extent of scalp area involved. The range is 0 to 72.

10.6 DIAGNOSIS AND ASSESSMENTS FOR PATIENTS WITH PSORIATIC ARTHRITIS (AT SELECTED SITES ONLY)

At Visit 1 at selected study sites, patients with a positive history of PsA or suspected to have PsA will be further evaluated for PsA diagnosis based on CASPAR (ClASsification of Psoriatic Arthritis) criteria ([R15-1001](#)).

To be classified as having PsA, a patient must have inflammatory articular disease (joint, spine, or enthesal) with at least 3 points total from the 5 categories in Table 10.6: 1. All trial participants will have 2 points assigned due to evidence of current psoriasis per trial entry criteria and will require at least one additional point for diagnosis of PsA.

Table 10.6:1 CASPAR criteria

Category	Point assignment
Evidence of current psoriasis, a personal history of psoriasis, or a family history of psoriasis	2 points
Typical psoriatic nail dystrophy, including onycholysis, pitting, or hyperkeratosis observed on current physical examination	1 point
A negative test result for rheumatoid factor by any method except latex	1 point
Either current dactylitis, defined as swelling of an entire digit, or a history of dactylitis recorded by a rheumatologist	1 point
Radiographic evidence of juxta-articular new bone formation appearing as ill-defined ossification near joint margins (but excluding osteophyte formation) on plain radiographs of the hand or foot	1 point

If a diagnosis of PsA is confirmed by CASPAR and the patient meets all study entry criteria for participation, the following will be performed at Visit 2.

- HAQ-DI (see [Appendix 10.7.2](#))
- Pain VAS (see [Appendix 10.7.3](#))
- Patient global assessment VAS (see [Appendix 10.7.4](#))
- Tender or Swollen joint counts (TJC/SJC) on 28 joints (refer to [Table 10.6: 2](#))
- Entry of data for calculation of DAS28 on electronic device (Refer to [Appendix 10.6.1](#))

During the treatment period and EOO the following will continue to be performed at the visits noted in the Flow Charts if the TJC/SJC is ≥ 3 at Visit 2.

- HAQ-DI (see Appendix 10.7.2)
- Pain VAS (see Appendix 10.7.3)
- Patient global assessment VAS (see Appendix 10.7.4)
- Tender or Swollen joint counts (TJC/SJC) on 28 joints (refer to Table 10.6: 2)
- Entry of data for calculation of DAS28 on electronic device (Refer to Appendix 10.6.1)

Proprietary confidential information © 2016 Boehringer Ingelheim International GmbH or one or more of its affiliated companies
Table 10.6:2 Tender or Swollen Joint Count (28)

Joint	Right		Left	
	Tender	Swollen	Tender	Swollen
Shoulder				
Elbow				
Wrist				
MCP1				
MCP2				
MCP3				
MCP4				
MCP5				
IP of the thumb				
PIP of fingers 2				
PIP of fingers 3				
PIP of fingers 4				
PIP of fingers 5				
Knee				

Metacarpal-phalangeal joints (MCP); Interphalangeal joints (IP); Proximal interphalangeal joints (PIP)

Tenderness and swelling will be evaluated as "0" absent or "1" present.

10.6.1 Disease Activity Score in 28 Joints (DAS 28)

DAS28, which stands for "disease activity score," is a modified version of the original DAS. DAS28 will be calculated using a formula that includes the number of tender joints and swollen joints (28 joints), CRP (C-reactive protein) and a patient self-assessment (patient global health-VAS).

DAS 28 will be calculated using the following formula from the electronic device where the VAS pertains to the patient's global assessment of disease VAS:

- $$\text{DAS28} = 0.56 * \sqrt{\text{(tender joint count)}} + 0.28 * \sqrt{\text{(swollen joint count)}} + 0.36 * \text{Ln}(\text{CRP}+1) + 0.014 * \text{(patient global assessment VAS)} + 0.96$$

For the DAS 28 calculation, the CRP value from laboratory report of current visit will be entered on the electronic device. Data from swollen and tender joint count (28 joints) and the patient global assessment VAS will have already been recorded on the electronic device.

10.7 HEALTH OUTCOMES/QUALITY OF LIFE

10.7.1 Dermatology Life Quality Index

The DLQI is a patient-administered, ten-question, quality of life questionnaire that covers six domains including symptoms and feelings, daily activities, leisure, work and school, personal relationships and treatment ([R05-2548](#)). The DLQI has a one-week recall period. Response categories include “not relevant” (score of 0), “not at all” (score of 0), “a little” (score of 1), “a lot” (score of 2) and “very much” (score of 3). Question 7 is a “yes”/“no” question where “yes” is scored as 3.

The DLQI will be self-administered by the patient at visits indicated in the flowchart.

The DLQI will be analysed under six headings as follows ([R05-2548](#)):

Domain	Question Number	Score
Symptoms and feelings	Questions 1 and 2	Score maximum 6
Daily activities	Questions 3 and 4	Score maximum 6
Leisure	Questions 5 and 6	Score maximum 6
Work and school	Question 7	Score maximum 3
Personal relationships	Questions 8 and 9	Score maximum 6
Treatment	Question 10	Score maximum 3

DLQI total score is calculated by summing the scores of each question resulting in a range of 0 to 30 where 0-1 = no effect on patient’s life, 2-5 = small effect, 6-10 = moderate effect, 11-20 = very large effect, and 21-30 = extremely large effect on patient’s life. The higher the score, the more the quality of life is impaired. If the answer to one question in a domain is missing, that domain is treated as missing. If 2 or more questions are left unanswered (missing), DLQI total score is treated as missing. A 5-point change from baseline is considered a clinically important difference.

DERMATOLOGY LIFE QUALITY INDEX

DLQI

Hospital No: Date: Score:
Name:
Address: Diagnosis:

The aim of this questionnaire is to measure how much your skin problem has affected your life
OVER THE LAST WEEK. Please tick one box for each question.

1. Over the last week, how itchy, sore, painful or stinging has your skin been?	Very much 	A lot 	A little 	Not at all 
2. Over the last week, how embarrassed or self conscious have you been because of your skin?	Very much 	A lot 	A little 	Not at all 
3. Over the last week, how much has your skin interfered with you going shopping or looking after your home or garden?	Very much 	A lot 	A little 	Not at all  Not relevant 
4. Over the last week, how much has your skin influenced the clothes you wear?	Very much 	A lot 	A little 	Not at all  Not relevant 
5. Over the last week, how much has your skin affected any social or leisure activities?	Very much 	A lot 	A little 	Not at all  Not relevant 
6. Over the last week, how much has your skin made it difficult for you to do any sport?	Very much 	A lot 	A little 	Not at all  Not relevant 
7. Over the last week, has your skin prevented you from working or studying?	Yes 	No  Not relevant 		
	If "No", over the last week how much has your skin been a problem at work or studying?	A lot 	A little 	Not at all 
8. Over the last week, how much has your skin created problems with your partner or any of your close friends or relatives?	Very much 	A lot 	A little 	Not at all  Not relevant 
9. Over the last week, how much has your skin caused any sexual difficulties?	Very much 	A lot 	A little 	Not at all  Not relevant 
10. Over the last week, how much of a problem has the treatment for your skin been, for example by making your home messy, or by taking up time?	Very much 	A lot 	A little 	Not at all  Not relevant 

Please check you have answered EVERY question. Thank you.

©AY Finlay, GK Khan, April 1992 www.dermatology.org.uk, this must not be copied without the permission of the authors.

10.7.2 Health Assessment Questionnaire Disability Index (HAQ-DI)

The HAQ-DI will be self-administered by the patient [for psoriatic arthritis patients at selected sites] at visits indicated in the flowchart.

The HAQ-DI is a twenty-item patient reported outcome instrument that assesses current physical function/ disability. The HAQ-DI covers eight categories (dressing and grooming, hygiene, arising, reach, eating, grip, walking and common daily activities). There are four response options, ranging from 0 (no difficulty) to 3 (unable to do). HAQ-DI score is reported as a mean score between 0 and 3 by dividing the total score by the number of items answered ([R15-3849](#)).

The HAQ-DI has been the most-widely used instrument to assess physical function clinical trials of treatments for rheumatoid and psoriatic arthritis and has extensive evidence of its validity and other psychometric properties in this context ([R15-3846](#)).

HEALTH ASSESSMENT QUESTIONNAIRE

Name _____

Date _____

PATKEY# _____
QUESTDAT _____

In this section we are interested in learning how your illness affects your ability to function in daily life. Please feel free to add any comments on the back of this page.

HAQADMIN _____

Please check the response which best describes your usual abilities **OVER THE PAST WEEK**:

QUESTYPE _____

	Without ANY Difficulty	With SOME Difficulty	With MUCH Difficulty	UNABLE To Do
--	------------------------------	----------------------------	----------------------------	-----------------

PMSVIS _____

DRESSING & GROOMING

RASTUDY _____

Are you able to:

QUESTNUM _____

- Dress yourself, including tying shoelaces and doing buttons?
- Shampoo your hair?

_____ _____ _____ _____

DRESSNEW _____

ARISING

Are you able to:

_____ _____ _____ _____

RISENEW _____

- Stand up from a straight chair?
- Get in and out of bed?

_____ _____ _____ _____

EATING

EATNEW _____

Are you able to:

_____ _____ _____ _____

- Cut your meat?
- Lift a full cup or glass to your mouth?
- Open a new milk carton?

_____ _____ _____ _____

WALKING

WALKNEW _____

Are you able to:

_____ _____ _____ _____

- Walk outdoors on flat ground?
- Climb up five steps?

_____ _____ _____ _____

Please check any AIDS OR DEVICES that you usually use for any of these activities:

 Cane	 Devices used for dressing (button hook, zipper pull, long-handled shoe horn, etc.)
 Walker	 Built up or special utensils
 Crutches	 Special or built up chair
 Wheelchair	 Other (Specify: _____)

DRSGASST _____

RISEASST _____

Please check any categories for which you usually need HELP FROM ANOTHER PERSON:

 Dressing and Grooming	 Eating
 Arising	 Walking

EATASST _____

WALKASST _____

Proprietary confidential information © 2016 Boehringer Ingelheim International GmbH or one or more of its affiliated companies

Please check the response which best describes your usual abilities OVER THE PAST WEEK:

	Without ANY Difficulty	With SOME Difficulty	With MUCH Difficulty	UNABLE To Do	
HYGIENE					
Are you able to:					
- Wash and dry your body?	—	—	—	—	
- Take a tub bath?	—	—	—	—	
- Get on and off the toilet?	—	—	—	—	HYGNNEW_____
REACH					
Are you able to:					
- Reach and get down a 5 pound object (such as a bag of sugar) from just above your head?	—	—	—	—	
- Bend down to pick up clothing from the floor?	—	—	—	—	REACHNEW_____
GRIP					
Are you able to:					
- Open car doors?	—	—	—	—	
- Open jars which have been previously opened?	—	—	—	—	
- Turn faucets on and off?	—	—	—	—	GRIPNEW_____
ACTIVITIES					
Are you able to:					
- Run errands and shop?	—	—	—	—	
- Get in and out of a car?	—	—	—	—	
- Do chores such as vacuuming or yardwork?	—	—	—	—	ACTIVNEW_____
Please check any AIDS OR DEVICES that you usually use for any of these activities:					
 Raised toilet seat	 Bathtub bar				
 Bathtub seat	 Long-handled appliances for reach				
 Jar opener (for jars previously opened)	 Long-handled appliances in bathroom				
 Other (Specify: _____)					
Please check any categories for which you usually need HELP FROM ANOTHER PERSON:					
 Hygiene	 Gripping and opening things				
 Reach	 Errands and chores				
HYGNASST_____					
RCHASST_____					
GRIPASST_____					
ACTVASST_____					

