10.3.3 Further Efficacy Endpoints

The further endpoints are as follows:

- Achievement of PASI 50 at all visits collected
- Achievement of PASI 75 at all visits collected
- Achievement of PASI 90 at all visits collected
- Achievement of PASI 100 at all visits collected
- Time to the first achievement of PASI 50, PASI 75, PASI 90, and PASI 100
- Time to loss of PASI 50, PASI 75, PASI 90, and PASI 100 response for subjects re-randomized at Week 28
- Change and percent change from baseline in PASI at all visits collected
- Achievement of PASI < 3 at all visits collected
- Proportion of subjects with at least 25% increase in PASI from baseline within 60 days after re-randomization for subjects re-randomized to placebo at Week 28
- Achievement of sPGA of clear or almost clear at all visits collected
- Achievement of sPGA of clear at all visits collected
- Time to the first achievement of sPGA of clear or almost clear
- Time to loss of sPGA of clear or almost clear response for subjects re-randomised at Week 28
- Time to sPGA of ≥ 3 (relapse) for subjects re-randomised at Week 28
- Change from baseline in DLQI at all visits collected

- Achievement of a DLQI score of 0 or 1 at all visits collected
- Achievement of a reduction of 5 or more points from baseline in DLQI score at all visits collected, among subjects with baseline $DLQI \geq 5$
- Change from baseline in HAQ-DI at all visits collected, among subjects with PsA confirmed via ClASsification of Psoriatic Arthritis (CASPAR) and had baseline value > 0
- Achievement of a reduction of 0.3 or more from baseline HAQ-DI at all visits collected, among subjects with PsA confirmed via CASPAR and had baseline value ≥ 0.3
- Change and percent change from baseline on patient Pain VAS, among subjects with PsA confirmed via CASPAR and had baseline value > 0
- Achievement of a reduction of 10 or more from baseline Pain VAS at all visits collected, among subjects with PsA confirmed via CASPAR and had baseline value ≥ 10
- Change and percent change from baseline on patient Global Assessment VAS, among subjects with PsA confirmed via CASPAR and had baseline value > 0
- Change from baseline in Swollen or Tender Joint Count (28 joints) at all visits collected, among subjects with PsA confirmed via CASPAR and had baseline value > 0
- Change from baseline in DAS28 at all visits collected, among subjects with PsA confirmed via CASPAR and had baseline value > 0

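### The protocol's HAQ-DI score is a mean over items that uses neither the eight categories nor the aid and help answers on its own form, and the SAP applies 0.3 cut-offs to it without a scoring rule

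*Protocol*

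**What the plan says.** Protocol 10.7.2 describes the instrument in two ways: "The HAQ-DI is a twenty-item patient reported outcome instrument", and "The HAQ-DI covers eight categories". Each item is answered from 0 to 3. The scoring sentence is "HAQ-DI score is reported as a mean score between 0 and 3 by dividing the total score by the number of items answered", with R15-3849 cited as its source.

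The form printed in the same section has one code field per category (DRESSNEW, RISENEW, EATNEW, WALKNEW, HYGNNEW, REACHNEW, GRIPNEW, ACTIVNEW) and one field ending in ASST per category. It also asks two further kinds of question: "Please check any AIDS OR DEVICES that you usually use for any of these activities" and "Please check any categories for which you usually need HELP FROM ANOTHER PERSON". Neither document says how any of these enters the score.

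Protocol 7.5 refers missing questionnaire items to Section 10.7. For the HAQ-DI, 10.7.2 offers only the division by items answered. For the DLQI, by contrast, 10.7.1 treats the total as missing once two or more questions are unanswered.

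SAP 10.3.3 analyses change in HAQ-DI and adds a responder endpoint, "Achievement of a reduction of 0.3 or more from baseline HAQ-DI at all visits collected", restricted to CASPAR-confirmed patients who "had baseline value ≥ 0.3". The SAP contains no HAQ-DI scoring rule and gives no source for 0.3.

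**The concern.** The scoring sentence and the form do not fit together. The form gathers information by category and by reliance on aids or people, while the score is a flat average of 20 items. The weight of a category then depends on how many items it happens to hold, the aid and help answers are collected but unused, and there is no floor on how little of the questionnaire must be completed.

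At stake is the physical-function measure for the psoriatic arthritis objective (Protocol 2.2 and 5.2). The SAP's responder endpoint applies 0.3 twice to this score, so both who enters that analysis and who counts as a responder depend on the derivation.

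**Working it through.** **Inputs.** Items per category, counted on the form in Protocol 10.7.2: dressing 2, arising 2, eating 3, walking 2, hygiene 3, reach 2, grip 3, activities 3. Cut-offs of 0.3 from SAP 10.3.3.

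**Reproducing the stated figures.** 2+2+3+2+3+2+3+3 = 20 items in 8 categories. A mean of answers from 0 to 3 lies between 0 and 3. Both agree with the protocol.

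**What follows from the rule as written (no outside rule needed).**
- Weighting: the four three-item categories hold 4 × 3 = 12 of 20 items, or 60%; the four two-item categories hold 8 of 20, or 40%. Each three-item category weighs 3/20 = 15% and each two-item category 2/20 = 10%. Equal weighting would give 1/8 = 12.5%.
- Aids and help: a patient with every item at 1 scores 20/20 = 1.00 whether aids and help are ticked everywhere or nowhere. If that reliance disappears and the item answers stay the same, the change is 1.00 − 1.00 = 0.
- Missing items: if only one item is answered, at 2, the score is 2/1 = 2.00. With the other 19 items answered 0, it would be 2/20 = 0.10.

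**Comparison with a category score.** The documents give no category rule. For illustration, assume each category takes its worst item and the score is the sum over 8, ignoring aids and help.

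| Answers | Item mean | Category mean |
|---|---|---|
| One item = 1 in each of 3 categories | 3/20 = 0.15 | 3/8 = 0.375 |
| One item = 1 in all 8 categories | 8/20 = 0.40 | 8/8 = 1.00 |
| All items = 1 | 20/20 = 1.00 | 8/8 = 1.00 |
| All items = 1 in the four three-item categories, others 0 | 12/20 = 0.60 | 4/8 = 0.50 |

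The first patient fails the baseline cut under the item mean and passes it under the category mean. The last row shows that the order can reverse. With answers of 1 only, reaching 0.3 takes 0.3 × 20 = 6 items under the protocol rule, and 0.3 × 8 = 2.4, so 3 categories, under the assumed rule.

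Reductions, for patients whose baseline is at least 0.3 under both rules:
- From all items = 1 to one item = 1 per category: 1.00 − 0.40 = 0.60 (responder) against 1.00 − 1.00 = 0 (non-responder).
- From one item = 1 per category to three of those categories cleared: 0.40 − 0.25 = 0.15 (non-responder) against 1.00 − 0.625 = 0.375 (responder).

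**Typical size.** Answers were simulated from correlated normal variables on the 20-item layout, under the same worst-item assumption and with no aids. Disability level and correlation are assumed, because the documents give neither.

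| Inter-item correlation | Item mean | Category mean | Gap | Share ≥ 0.3, item mean vs category mean |
|---|---|---|---|---|
| 0.4 | 0.38 | 0.67 | 0.29 | 51% vs 70% |
| 0.6 | 0.39 | 0.63 | 0.24 | 45% vs 60% |
| 0.75 | 0.38 | 0.56 | 0.18 | 41% vs 52% |

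Eight further settings covered average item means from 0.07 to 0.99. The item mean was lower on average in all of them, with gaps from 1.409 − 0.994 = 0.42 down to 0.122 − 0.074 = 0.05. It exceeded the category mean in under 0.5% of simulated patients.

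**The case against.** The strongest reply is that the protocol does state a rule and cites R15-3849 for it. That source is not available here, and its title covers both the HAQ and an improved HAQ, so the item mean cannot be called a misreading of it. The code fields on the form are not explained and stand beside administrative codes, so they do not by themselves prove a category score. The same rule applies in both arms and does not by itself bias the randomised comparison. All of this stands.

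A reader might go further and infer that HAQ-DI scores run too low against 0.3, that patients will less often reach the 0.3 reduction, or that 0.3 belongs to another scale. The documents do not support these readings. *Too low* needs a reference rule that neither document contains. The two worked reductions show responder status moving in opposite directions. Nothing in the SAP links 0.3 to any particular scoring.

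The reply does not explain why aid and help answers are collected and then left out, and it does not supply a minimum for completeness. Protocol 7.5 may be meant to bring in the instrument's own instructions, but the section it points to sets no limit.

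**Conclusion.** The point holds as a minor fault in a stated derivation. Three consequences follow from the documents alone: 60% of the weight falls on four of the eight categories, a change in reliance on aids or help registers as zero, and one answered item produces a score. The SAP then applies 0.3 cut-offs to that score without defining it.

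The size relative to a category score rests on the worst-item assumption and on invented disability levels. On that basis the item mean is usually lower, by about 0.2 to 0.3 where the average item mean is near 0.38, and responder status at 0.3 can go either way.

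Reach is limited. HAQ-DI is a further endpoint (Protocol 5.1.3, SAP 10.3.3) in CASPAR-confirmed patients at selected sites, and under Protocol 10.6 it continues after Visit 2 only with a joint count of at least 3. No primary or ranked secondary endpoint, alpha level or sample-size figure depends on it.

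**What to change.** In Protocol 10.7.2 and in the SAP, derive one score for each of the eight categories using that category's aid and help answers, and average over the categories answered. Take the exact category rule and the missing-data rule from the cited instructions (R15-3849) and write them out. If those instructions turn out to prescribe the item mean for this form, say so, and state that the aid and help answers do not enter.

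State in SAP 10.3.3 that both 0.3 cut-offs apply to the score so defined. Keep the item mean as a sensitivity analysis, since it is the rule now on record. Because the questionnaire is completed electronically, confirm that the eCOA export holds the item, aid and help fields and not just a total.

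The cost is wording in two documents, a short derivation program and rescoring of earlier visits. If the export holds those fields, no new data are needed.
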